Randomization	
Data collected at the screening visit are used to assign participants to intervention groups. Matched groups are randomized to the interventions to minimize differences between intervention groups in these baseline characteristics. Based on sex (2 levels: male, female), age (3 levels: 18–34, 35–49, 50–65), Body Mass Index (BMI) (2 levels: 18.5–24.9, 25–30 kg/m²) and sweet liker phenotype (3 levels: sweet liker, inverted U, sweet disliker), in a process of stratified randomization (2×3×2×3=36 strata). Treatment allocation is performed according to a computer-generated random schedule, at the ratio 1:1:1 to each of the three groups. Treatment allocation is performed by an independent person, not involved in the study outcome assessments or statistical analyses.

Sample size	
The sample size calculation is based on our primary outcome: change in preference score from 0–6 months. Previous studies have established that it is possible to detect shifts in preferred concentration from preference tests. For example, looking at the study of Liem and [name] (2004) and the change in most preferred concentration, we can observe that mean ranking score for the sweet exposure group changed by around 0.4 and by around 0.6 for the sour exposure group from baseline to after exposure, which is around 10%. Therefore, the effect size of 0.1 was considered to be a relevant and meaningful effect size for our study and was used to estimate the sample size. We estimate that 147 participants are needed to detect an effect size of 0.1, assuming a parallel study with 3 groups, with two repeated measures (baseline vs 6-month, correlation between measures of 0.7), and a

	power of 80% at a significance level of 0.05. To account for a potential dropout of 20%, 180 individuals will be enrolled in the study.																																																																																																																																																																																									
Statistical interim analysis	No interim analyses will be carried out.																																																																																																																																																																																									

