Adherence and Protocol deviations	Adherence to diets will be assessed on group level with biomarkers of sweetener consumption in 24-h urine sample, and 24h recalls.

STATISTICAL ANALYSIS	
Analysis methods	
Data will be analyzed in R. Based on findings of previous studies (Liem and [name], 2004), we do not expect the data to be non-normally distributed. Descriptive statistics will be provided for each of the three intervention groups at baseline and will include demographic, dietary and lifestyle information. Continuous data will be summarized using means, SD/SE and 95% confidence intervals or median/geometric means and back-transformed 95% CI's if not normally distributed. Categorical variables will be summarized using counts and percentages.
 
Analysis will be conducted on both an intention-to- treat (ITT) and a per-protocol basis. The ITT analysis will be the primary analysis. The per-protocol analysis (participants who finished the study), will help us determine whether the effects are the result of individuals adhering to the procedure and consuming the provided intervention foods. In the event of missing data due to drop-out, the outcome variables that have not been recorded will be treated as missing data. Unblinding will occur at the conclusion of the study to determine the effect of the intervention. Unblinding will take place in two steps: initially disclosing the allocation of individuals to their respective groups, without indicating intervention allocation. Only after the primary analyses have been conducted we will unblind the identity of each group.
 
Primary outcome:
 
To determine whether there is a shift in sweetness preference between baseline and month 6, statistical techniques appropriate for longitudinal data analysis, that is linear mixed effects models, will be used, with treatment (LSE, RSE and HSE), time (baseline, 1, 3, 6, 7 and 10-months) as fixed factors, the interaction between treatment x time outcome and participant number as a random factor. Our main interest is in the change in preference score between 0 and 6 months of any two intervention groups. The interaction effect will be evaluated to indicate if the change differed between the groups. If significant, the following predefined contrasts will be calculated: baseline vs. month 6 and LSE vs. RSE vs. HSE with all possible combinations. Subsequent, pairwise post-hoc tests will be Bonferroni adjusted.

Other outcomes:

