Similar linear mixed effects models will be used to explore effects of sweet taste exposure on the other dependent measures over time (baseline, 1, 3, 6, 7 and 10-months). The interaction effect (intervention group x time) will be evaluated to indicate if the pattern of change of a certain outcome differed between the groups. If significant, the following predefined contrasts will be calculated: baseline vs. 1 vs. 3 vs. 6 vs. 7 vs. 10-months and LSE vs. RSE vs. HSE with all possible combinations.

In light of the research in this area, we will explore differences between intervention groups and secondary outcome variables and explore related but separate questions of whether glucose variability, body composition, food cravings, blood biomarkers are related to sweetness exposure, age, gender, sweet liker status and BMI.

By comparing group means of urine extraction of urinary sucrose, fructose, and LCSs between intervention groups, the level of compliance will be evaluated. Linear mixed effects models will be adjusted for covariates where appropriate and both unadjusted and adjusted models will be reported. If interaction effect between time and intervention are identified, Posthoc tests (with Bonferroni adjustments) will be applied to identify statistically significant differences.

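### The primary model leaves out the four factors used to stratify randomisation, and the SAP does not fix the covariates or say which model decides; some precision may be lost

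*SAP*

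**What the plan says.** Under Study Methods, Randomization, the SAP allocates participants "in a process of stratified randomization (2×3×2×3=36 strata"), using screening data on sex (2 levels), age (3), BMI (2) and sweet-liker phenotype (3), "at the ratio 1:1:1 to each of the three groups". The stated aim is to keep the arms alike on these characteristics.

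Under Statistical Analysis, Primary outcome, the model is specified "with treatment (LSE, RSE and HSE), time (baseline, 1, 3, 6, 7 and 10-months) as fixed factors", with "the interaction between treatment x time outcome and participant number as a random factor". No stratification factor appears. The target is given as: "Our main interest is in the change in preference score between 0 and 6 months of any two intervention groups".

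Under Other outcomes, after the sentence on urinary compliance markers, the SAP adds: "Linear mixed effects models will be adjusted for covariates where appropriate and both unadjusted and adjusted models will be reported". The paragraph before it mentions age, gender, sweet-liker status and BMI, but only as variables for exploratory questions about secondary outcomes.

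**The concern.** When allocation is balanced on factors that predict the outcome, the analysis normally includes those factors. Otherwise the variation they explain stays in the residual, and precision that the stratification could have given is not used. Here the SAP writes the model out in full and omits them, so this is not a detail left to the protocol.

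The covariate sentence does not close the gap. If it covers only the other outcomes, the primary model stays unadjusted. If it also covers the primary outcome, there will be two primary results, an open choice of covariates and no rule for which result counts. Either reading needs a decision before the groups are unblinded.

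**Working it through.** **Inputs from the SAP.** 3 arms, 2 measures, correlation 0.7, effect size 0.1, alpha 0.05, power 80%, 147 evaluable, 180 enrolled, 36 strata (180/36 = 5 participants per stratum on average). **Assumed:** R2, the share of variance in the 0-6 month change explained by the four factors, from 0 to 30%.

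**1. The plan's own figure.** The SAP states: "We estimate that 147 participants are needed to detect an effect size of 0.1", "with two repeated measures (baseline vs 6-month, correlation between measures of 0.7"). Reading 0.1 as Cohen's f for a within-between interaction, lambda = f² × N × m/(1 − rho) = 0.01 × 147 × 2/0.3 = 9.8, with 2 and 144 df. Power is 0.798 at N = 147 and 0.801 at N = 148. The figure reproduces.

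**2. Main effects alone do almost nothing.** A factor effect that is constant within a participant enters the month-0 and month-6 scores equally and cancels from their difference. Six-visit random-intercept models were fitted to simulated data (180 participants, correlation 0.7, factors explaining 30% of between-person variance, 8 data sets per case). The standard error (SE) of the 0-6 between-arm contrast was:

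| Case | As written | + main effects | + factor × visit |
|---|---|---|---|
| Complete data, factors unrelated to change | 0.1418 | 0.1418 | 0.1422 |
| 20% dropout, factors unrelated to change | 0.1504 | 0.1501 | 0.1507 |
| Complete data, factors predict month-6 change | 0.1448 | 0.1448 | 0.1435 |
| 20% dropout, factors predict month-6 change | 0.1530 | 0.1527 | 0.1514 |

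With complete data, main effects left the estimates identical as well. Any gain needs the factor × visit terms.

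**3. Possible gain in a change-score test.** With factor × visit terms, lambda becomes 9.8/(1 − R2), the SE is multiplied by √(1 − R2), and 6 df are used (147 − 3 − 6 = 138). This was checked by simulation, 6,000 runs per case: 180 randomised in blocks of 3 within 36 unequal strata, 147 completers, 2-df test on change, effect set for 80% power. Block size and stratum frequencies are assumptions.

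| R2 | SE ratio | Power by formula, adjusted | Simulated, unadjusted | Simulated, adjusted |
|---|---|---|---|---|
| 0 | 1.000 | 79.8% | 80.6% | 80.0% |
| 5% | 0.975 | 81.9% | 79.1% | 80.5% |
| 10% | 0.949 | 84.1% | 80.1% | 83.8% |
| 20% | 0.894 | 88.3% | 80.8% | 88.0% |
| 30% | 0.837 | 92.2% | 81.8% | 92.3% |

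Further simulations gave 81% against 84% at R2 = 10% and 80-81% against 88% at R2 = 20%. At R2 = 0 they showed a loss of 1 point (80% against 79%; 79% against 78%).

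**4. Gain in the planned model.** The planned random-intercept model pools residual variance over six visits, which dilutes an effect on the 0-6 change. In the third row of the first table the factors add variance 0.25² = 0.0625 to a change variance of 2 × 0.3 = 0.6, so R2 = 0.0625/0.6625 = 9.4%. A change-score test would cut the SE by 1 − √(1 − 0.094) = 4.8%. The six-visit model cut it by 1 − 0.1435/0.1448 = 0.9%. In that example the factors act at month 6 only. Simulated power gains in the six-visit model were about 0-3 points.

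**5. Parameters added.** The factors need 1 + 2 + 1 + 2 = 6 main-effect terms and 6 × 5 = 30 interactions with visit, 36 in all. That this equals the number of strata is a coincidence.

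**The case against.** The strongest reply is that nothing promised is lost. Simulated unadjusted power stays between 79% and 82% at every R2, so the design keeps its 80% and adjustment would be a bonus. The SAP's reason for stratifying is baseline balance, not prediction of change, and it gives no R2. The covariate sentence is worded generally enough to reach the primary model. All of this stands as a limit on size. None of it says which covariates enter or which model decides.

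A reader might infer something stronger: that the planned error bars are too wide and the planned test is conservative. The SAP does not support that. In the change-score test with blocks of 3, unadjusted size does fall, to about 3.1% at R2 = 20%. But that is not the planned test. For the 0-6 contrast in the six-visit random-intercept model under compound symmetry, one simulation at R2 = 20% gave unadjusted size of 4.3%, and another gave about 5-6%. With correlation that decays between visits, sizes were 6-10% in the first and 9-10% in the second. The direction depends on a covariance pattern that the SAP does not describe; its only correlation is 0.7.

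The cost objection also stands in part: 36 parameters is more than a token addition, and the same terms would be heavy in the glucose-sensor subgroup. With 60 people, 20 per arm and three visits, they would need 6 + 6 × 2 = 18 covariate parameters, and no check supports that.

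**Conclusion.** The omission holds: four factors govern allocation, none is in the stated primary model, and the SAP names neither the covariates of an adjusted model nor the deciding model. The loss of precision is conditional on R2. For R2 of 10-20% it is worth about 3-7 points of power in a change-score test and about 0-3 points in the planned six-visit model. If the factors explain none of the change, leaving them out costs nothing. The figures rest on the assumed R2, blocks of 3 and assumed stratum frequencies; the six-visit figures also depend on the covariance pattern. No claim is made about the direction of any type I error. This is a modest improvement to specification, not a threat to validity.

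**What to change.** In the primary model, add sex, age group, BMI group and sweet-liker phenotype as classified at screening for randomisation, not as re-measured later. Enter each as a main effect and in interaction with visit, as additive terms rather than 36 cells. Declare this the primary analysis and keep the unadjusted model as supportive. State whether the covariate sentence under Other outcomes applies to the primary outcome. The same terms can be used for the other full-sample outcomes, but should not be imposed on the 60-person glucose subgroup.

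Cost: SAP wording only, since the factors are already recorded for allocation; 36 extra fixed parameters over six visits; and up to about 1 point of power if the factors explain nothing. The change should be made before the first unblinding step.

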	Adverse events, medication use	Questionnaires ^b , Study diet diary	✓	✓	✓	✓	✓	✓																																																																																																																																																																																		

OUTCOMES		
Primary Outcome measure		
Outcome Measure	Measure Description	Time Frame
Change in preference score	Measured during preference testing, using Ranking on a scale methodology (scale anchored at 0: Dislike extremely; 50: Neither dislike or like; 100: Like extremely) in a series of test foods.	From month 0 to month 6.
Secondary Outcome measures		
Outcome Measure	Measure Description	Time Frame
Change in preference score.	Measured during preference testing, using Ranking on a scale methodology (scale anchored at 0: Dislike extremely; 50: Neither dislike or like; 100: Like extremely) in a series of test foods.	Measured at 0, 1, 3, 6, 7 and 10 months.
Difference in mean liking scores between familiar and unfamiliar foods.	Measured during preference testing, using Ranking on a scale methodology (scale anchored at 0: Dislike extremely; 50: Neither dislike or like; 100: Like extremely) in a series of test foods.	Measured at 0, 1, 3, 6, 7 and 10 months.
Change in sensory intensity scores.	Measured during sensory testing, using 100-unit Visual analogue scale (VAS), (anchored at 0: not sweet/salty at all; 100: Extremely sweet/salty) in a series of test foods.	Measured at 0, 1, 3, 6, 7 and 10 months.
Change in energy intake.	Measured during ad-libitum test meal in kcal.	Measured at 0, 1, 3, 6, 7 and 10 months.

Change in energy intake.	Measured during ad-libitum test meal in kJ.	Measured at 0, 1, 3, 6, 7 and 10 months.
Proportion of eaten sweet foods vs. foods from other taste modalities.	Measured during ad-libitum test meal in proportions.	Measured at 0, 1, 3, 6, 7 and 10 months
Sweet-liker status score.	Measured on a 100-unit VAS scale (anchored at 0: Dislike; 100: Like).	Measured at 0, 1, 3, 6, 7 and 10 months.
Food craving questionnaire scores.	Measured using the Control of eating questionnaire (CoEQ)	Measured at 0, 1, 3, 6, 7 and 10 months.
Taste preference questionnaire scores.	Measured using Taste Preference questionnaire (PrefQuest).	Measured at 0, 1, 3, 6, 7 and 10 months.
Dietary taste patterns.	Measured with the Taste food frequency questionnaire in frequency.	Measured at 0, 1, 3, 6, 7 and 10 months.

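### With participant as the only random factor over six unequally spaced visits, the standard error of the primary 0-6 month contrast rests on the average of 15 visit-pair correlations, so it may be too small, right or too large

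*SAP*

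**What the plan says.** In the SAP's table of primary outcome measures, the time frame is "From month 0 to month 6" and the score is obtained "in a series of test foods".

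Under Statistical Analysis, Analysis methods, Primary outcome, the linear mixed model has treatment and "time (baseline, 1, 3, 6, 7 and 10-months) as fixed factors", together with "the interaction between treatment x time outcome and participant number as a random factor". No random slope, residual correlation, visit-specific variance, robust standard error or degrees-of-freedom method is named.

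The same paragraph states the target: "Our main interest is in the change in preference score between 0 and 6 months of any two intervention groups". The treatment-by-time interaction is tested before the contrasts: "If significant, the following predefined contrasts will be calculated: baseline vs. month 6 and LSE vs. RSE vs. HSE". Then "Subsequent, pairwise post-hoc tests will be Bonferroni adjusted".

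The Sample size section gives the only correlation in the document, "with two repeated measures (baseline vs 6-month, correlation between measures of 0.7". Nothing is said about the other 14 visit pairs. The Other outcomes paragraph carries similar models over to the secondary outcomes.

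**The concern.** A random intercept with independent residuals estimates one residual variance from all visits and uses it for every within-participant contrast. That is right only if the variance of the difference is the same for every pair of visits. Here the visits are 1 to 10 months apart and extend past the end of the intervention, so a common correlation is a strong assumption. The primary contrast uses just one of the 15 pairs.

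If the 0-6 correlation differs from the average, the confidence intervals for the primary effect have the wrong width, and a Bonferroni adjustment does not repair a wrong standard error. The interaction test that decides whether the contrasts are calculated at all relies on the same assumption.

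**Working it through.** **Inputs from the SAP.** Visits at 0, 1, 3, 6, 7 and 10 months; three arms; 147 evaluable participants (49 per arm); r(0,6) = 0.7; alpha 0.05; effect size 0.1, read as Cohen's f. Every other correlation below is an assumption.

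**The plan's own figure.** For a group-by-time interaction with m = 2 measures, lambda = f² × N × m / (1 − r) = 0.01 × 147 × 2 / 0.3 = 9.8. The F test gives 79.8% power at N = 147 and needs 148 for 80%. The chi-square version gives 144.5, or 147 in three equal arms. The stated 147 is reproduced within rounding. It uses only the 0-6 pair, so this point does not affect it.

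**Visit pairs.** Six visits give 15 gaps: 1, 1, 2, 3, 3, 3, 4, 4, 5, 6, 6, 7, 7, 9, 10. Nine are under 6 months, two are 6 months and four are longer. The mean is 71/15 = 4.73 months.

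**Standard errors.** With complete data and equal visit variances (SD = 1), for the difference between two arms in 0-6 change:
- Model SE = sqrt(4 × (1 − mean r) / n).
- True SE = sqrt(4 × (1 − r(0,6)) / n) = sqrt(4 × 0.3 / 49) = 0.157.
- Ratio = sqrt((1 − mean r) / 0.3). Coverage = 1 − P(|Z| > 1.96 × ratio).

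Exponential fade means r(gap) = (1 − noise) × exp(−k × gap) with r(6) = 0.7. Noise of 0/10/20/25% gives a 1-month correlation of 0.94/0.86/0.78/0.74. Gentle fade is 0.75 to 3 months, 0.70 to 6 and 0.60 beyond, so mean r = (6 × 0.75 + 5 × 0.70 + 4 × 0.60)/15 = 0.693. Step fade is 0.70 to 6 months and 0.50 beyond, so mean r = (11 × 0.70 + 4 × 0.50)/15 = 0.647.

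The last column is the simulated type I error of the 10-df interaction test (random-intercept analysis, complete data, one score per participant-visit, 49 per arm, 100,000 null trials each).

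| Pattern | Mean r | SE ratio | 95% coverage | Interaction test |
|---|---|---|---|---|
| Exponential, no noise | 0.764 | 0.887 | 91.8% | 10.5% |
| Exponential, 10% noise | 0.743 | 0.926 | 93.0% | 7.6% |
| Exponential, 20% noise | 0.721 | 0.964 | 94.1% | 5.7% |
| Exponential, 25% noise | 0.711 | 0.982 | 94.6% | 5.2% |
| Flat 0.7 | 0.700 | 1.000 | 95.0% | 5.1% |
| Gentle fade | 0.693 | 1.011 | 95.2% | 6.1% |
| Step fade | 0.647 | 1.085 | 96.7% | 6.6% |

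**Full procedure: interaction test, then Bonferroni over three arm pairs.**
- Arms differ at no visit: false 0-6 claims in 5.2/3.1/1.9/1.5% of trials for noise 0/10/20/25%, 1.5% under gentle fade and 1.0% under step fade.
- Real differences at months 1 and 3 only (arms at −d, 0, +d; d = 0.2, 0.3 or 0.5 SD; 50,000 trials each): 8.5 / 6.7-7.2 / 5.3-5.6 / 4.8% for noise 0/10/20/25%, 3.9-4.2% gentle, 2.5-2.7% step.
- In the second setting with a Bonferroni family of 6 or 15, the maximum is 5.1% or 2.6%.

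**Same checks with an unstructured covariance** (complete-data equivalents: Wilks test, contrast on 144 df). In all patterns the interaction test and the single contrast are at 4.9-5.1%. The full procedure is at 1.2% under the null and 4.2-4.6% with real differences at months 1 and 3.

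**Three-visit outcomes (0, 6 and 10 months).** The sign reverses: the same exponential fades (noise 0-25%) make the 0-6 standard error 0.8-3.3% too large.

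**The case against.** The strongest reply is that no error is shown, only an unverified assumption. The SAP does not exclude a residual structure, and it promises methods suited to longitudinal data. Fourteen of the 15 correlations are assumed here, and depending on the choice the standard error comes out too small, exact or too large. This stands as a limit on what can be claimed. It does not rescue the text, because no structure is named and the plain reading is a random intercept.

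The raised false-claim rate also needs unusual conditions. Arms must differ at months 1 and 3 yet be equal at month 6, while the diets are still in force. In a more natural case, one arm differs at months 1, 3 and 6 and the other two are equal. False 0-6 claims were then 3.4-3.5% with no noise and 2.0-2.2% at 20% noise. The SAP's reference to all possible combinations may also mean a Bonferroni family larger than three. Both points stand.

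A reader might infer that the plan understates the primary standard error, or that its false-positive rate is about 10%. The documents support neither. The sign depends on correlations the SAP does not give, and the 10.5% belongs to the interaction test in the most extreme pattern tried, not to the primary claim.

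**Conclusion.** The point holds as a specification weakness with moderate, conditional consequences. On the plain reading, the primary standard error depends on 14 correlations about which the SAP says nothing. Its error ranged from 11% too small to 8.5% too large in the patterns tried. The interaction test was above its nominal level in every fading pattern, including those where the 0-6 standard error is too large.

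False primary claims stay at about 5% or below if the arms differ at no visit. They reach about 5.5-8.5% only when three conditions meet: real differences at other visits, absent at month 6, make the interaction significant; correlation fades exponentially with at most about 20% visit-level noise; and the Bonferroni family is three.

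These figures assume complete data, equal visit variances and one score per participant per visit. With dropout or unequal variances, the standard error rests instead on a weighted average of the variances of the pairwise differences. If each test food contributes its own row, the figures do not apply. The change should be made, but the point does not invalidate the design or the sample size.

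**What to change.** For the primary model, define one summary preference score per participant per visit. Prespecify an unstructured covariance over the six visits (6 × 7 / 2 = 21 parameters, for about 147-180 participants) with Kenward-Roger degrees of freedom. Name one fallback if it does not converge, for example a participant intercept with small-sample cluster-robust standard errors.

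Use the same approach for secondary outcomes with six or three visits (21 or 6 parameters). Body weight and 24-hour recall intake are listed at nine visits, which would need 9 × 10 / 2 = 45 parameters. For these, and for the glucose-sensor subset of 60, allow the fallback or a stated structured covariance.

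The cost is SAP wording and fewer error degrees of freedom: critical t about 1.977 on 144 df against 1.963 on 720, a factor of 1.007. Combined with the change in standard error, the 0-6 intervals would be about 2.5% (1.007/0.982) to 13.5% (1.007/0.887) wider under exponential fade. They would be about 0.4% (1.007/1.011) to 7% (1.007/1.085) narrower under gentle or step fade. Settling this before unblinding also avoids choosing the covariance after seeing the data.

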Statistical Analysis Plan (SAP)

Sweet Tooth: Nature or Nurture? Role of Long-term Dietary Sweetness Exposure on Sweetness Preferences

Version 2024.02.07 (yyyy.mm.dd)

GENERAL INFORMATION	
Principal investigator	Dr. [name] Sensory Science and Eating Behaviour Wageningen University and Research Wageningen, the Netherlands
Core team members	[name] [name] (Project leader) ¹ [name] (statistician) ¹ [name] ² [name] ¹ [name] ² [name] ² [name] ¹
	¹ Division of Human Nutrition and Health, Wageningen University and Research, Wageningen, The Netherlands
	² Department of Psychology, Faculty of Science and Technology, Bournemouth University, Bournemouth, United Kingdom
Name of project	Sweet Tooth
ClinicalTrials.gov identifier	NCT04497974
Project Registration number	NL72134.081.19
Ethical review	METC-nr 20/02, METC-WU

INTRODUCTION	
Objectives	
Primary objective: To assess the effect of a 6-month low, regular, and high dietary sweetness exposure on preference for sweet foods and beverages, and to compare these effects between the intervention groups.
 
Secondary Objective(s): To assess the effect of a 6-month low, regular, and high dietary sweetness exposure on taste intensity perception, behavioural outcomes: food choice and intake, sweet-like type, food cravings, dietary taste preferences, dietary taste patterns; anthropometric outcomes: body composition, waist-hip circumference, body weight; and biochemical outcomes: glucose variability, and biomarkers related to CVD and diabetes.

STUDY METHODS	
Trial design	
The Sweet Tooth study is a 6-month parallel randomized controlled trial with partial food provision. with three arms:
 
 1. a regular sweet exposure diet (RSE, control) (n=60); 2. a low sweetness exposure diet (LSE) (n=60); and 3. a high sweetness exposure diet (HSE) (n=60).

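### The primary 0–6 month comparisons depend on a six-visit, 10-df interaction test, but the trial was sized for a two-visit, 2-df test

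*SAP*

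**What the plan says.** - **Primary outcome** (SAP, Outcomes, Primary Outcome measure): change in preference score, with time frame "From month 0 to month 6".
- **Secondary outcome** (SAP, Outcomes, Secondary Outcome measures): the same score over all visits, "Measured at 0, 1, 3, 6, 7 and 10 months".
- **Sample size** (SAP, Sample size): "We estimate that 147 participants are needed to detect an effect size of 0.1", for three groups and "with two repeated measures (baseline vs 6-month, correlation between measures of 0.7", with 80% power at a significance level of 0.05.
- **Trial design**: "The Sweet Tooth study is a 6-month parallel randomized controlled trial with partial food provision". Months 7 and 10 are headed as follow-up in the visit table, so they fall after the intervention.
- **Primary analysis** (SAP, Analysis methods, Primary outcome): a linear mixed model with treatment, "time (baseline, 1, 3, 6, 7 and 10-months) as fixed factors", their interaction, and participant as a random factor. The stated aim is: "Our main interest is in the change in preference score between 0 and 6 months of any two intervention groups". The decision rule is: "The interaction effect will be evaluated to indicate if the change differed between the groups. If significant, the following predefined contrasts will be calculated". The contrasts that follow are baseline against month 6 for all pairs of arms, with Bonferroni adjustment of the pairwise tests.

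**The concern.** The outcome and the sample size concern two time points. The test that decides whether the primary contrasts are calculated concerns six. That mismatch has three consequences.

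1. The interaction test can miss a true 0–6 difference, because its power is spread over ten degrees of freedom and depends on what happens at months 1, 3, 7 and 10.
2. It can be significant for a reason unrelated to the primary question, namely a difference only after the intervention has ended.
3. If it is not significant, the plan provides no between-arm contrast for the primary outcome, although the primary objective is to compare the arms.

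The SAP gives no power and no assumed time course for the six-visit test. It also does not say which result, the interaction or a pairwise contrast, decides whether the primary hypothesis is met.

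**Working it through.** **Inputs from the SAP.** N = 147, three arms, 1:1:1 allocation (49 per arm), effect size 0.1, correlation 0.7 between baseline and month 6, alpha 0.05, six time levels in the model.

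**Assumptions of this review.** The effect size is Cohen's f (the SAP does not name the metric). The correlation is 0.7 between all visits, as a single random participant factor implies. Data are complete on 147. RSE lies midway between the other two arms. The Bonferroni family is the three pairwise differences in 0–6 change. The time courses are those in the table.

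**Step 1: degrees of freedom.** Sample size: (3−1)×(2−1) = 2. Planned model: (3−1)×(6−1) = 10.

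**Step 2: the SAP's own figure.** For the two-visit interaction, λ = N × 2 × f² / (1−ρ) = 147 × 2 × 0.01 / 0.3 = 9.8. With df 2 and 144, power is 79.8%. The SAP's 147 is reproduced within rounding, which supports the Cohen's f reading.

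**Step 3: the same 2-df question asked of the six-visit model.** An f of 0.1 at two visits corresponds to a root-mean-square arm deviation in change of 0.2 SD (arm effects −0.245, 0, +0.245 SD at month 6). For the joint month-6-minus-baseline contrast, λ = 147 × 0.2² / (2 × 0.3) = 9.8. With df 2 and 5 × (147−3) = 720, power is 80.5%, whatever happens at the other visits.

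**Step 4: the 10-df interaction.** λ = N × 0.04 × SS / 0.3, where SS is the sum of squared deviations, over the six visits, of the share of the month-6 effect present at each visit. The denominator df is 720. Two examples:
- Half the effect at months 1, 3, 7 and 10: SS = 0.5, λ = 147 × 0.04 × 0.5 / 0.3 = 9.8. This is the same λ as in step 2, but on 10 df the power is 52.6%.
- Full effect at months 1–6, none afterwards: SS = 1.5, λ = 29.4, power 98.0%.

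**Step 5: the full rule, by simulation** (20,000 trials per course). Linear means 1/6 of the effect at month 1 and 1/2 at month 3.

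| Course of the effect | Interaction significant | Interaction significant and at least one Bonferroni-3 contrast |
|---|---|---|
| Half at months 1, 3, 7, 10 (least favourable) | 52.1% | 50.4% |
| Linear, then 75% / 25% at months 7 / 10 | 71.8% | 65.3% |
| Linear, then 50% / 0 | 73.9% | 66.7% |
| Linear, then 0 | 78.5% | 69.3% |
| Month 6 only | 79.6% | 70.1% |
| Constant, months 1–10 | 79.8% | 70.0% |
| Linear, then persisting | 89.0% | 75.1% |
| Months 3–6 only | 96.1% | 77.5% |
| Months 1–6 only | 98.1% | 78.8% |

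Without the interaction condition, the same three contrasts have 78.4% to 79.4% power. If only one arm differs (0, 0, 0.424 SD, the same f), the full rule gives 50.5% to 77.1%, against 77.5% to 78.7% without the condition.

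**Step 6: completers needed for 80% under the planned rule** (8,000 trials per N, interpolated where needed). About 162 (linear then persisting), 174 (month 6 only), 189 (linear then 75%/25%) and 246 (least favourable), against 147 planned.

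**Step 7: false positives.** With no difference anywhere, a pairwise claim occurs in 4.1% of trials under Bonferroni-3 alone and 1.1% under the planned rule. The 2-df contrast rejects in 4.7%. With an effect at months 7 and 10 only, the interaction is significant in 96.3% of trials, and a false 0–6 pairwise claim follows in 4.3%.

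**The case against.** **The interaction might mean only its 0–6 part.** The sentence before the rule names the 0–6 change, and the SAP describes the interaction for the other outcomes as concerning the pattern over time. That reading is possible, but the SAP defines no such test. The only interaction it specifies is treatment by a six-level time factor, and the 0–6 contrasts come after it. If the narrower test was meant, the same edit is needed.

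**The sample size powers an interaction test, so compare like with like.** On that basis the 10-df test alone has 53% to 98% power. It matches or exceeds the planned 79.8%, to rounding, in five of the nine courses, is at 78.5% in a sixth, and falls clearly short in three. This stands: power is not always below 80%, and the 50% figure is the mathematical minimum rather than an expected course. But the SAP's stated interest is in differences between pairs of arms, which needs the contrasts as well. For that, the rule stayed below 80% in every course tried.

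**The Bonferroni family is not fixed at three.** This is correct. If all 15 pairs of the six arm-by-visit means were compared, power without the interaction condition would be about 59%. The condition would then cost about 0 to 5 points in four of the five courses tried, and more in the least favourable (59% to 47%). The loss due to the condition therefore depends on the family, which is a further reason to name the contrasts.

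**An estimate could be read from the fitted model.** True, since its terms contain the 0–6 differences. But the SAP makes calculation of the contrasts conditional.

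**Omnibus test first is conventional and conservative.** It is, but the contrasts are already Bonferroni adjusted, so error control does not need it. The false-positive consequence is small. What remains is the risk that a significant interaction driven by months 7 and 10 is reported by itself as showing that the 0–6 change differed.

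**Conclusion.** Wrong as written. The condition placed on the primary contrasts tests a different and wider hypothesis than the primary outcome and the sample size, and 80% power is not established for it. Under the assumptions listed, the planned rule has 50% to 79% power, against about 79% for the same contrasts without the condition and about 80% for the direct 2-df test. The loss is up to about 29 points, some 9 to 14 points in the linear courses that fade after month 6, and almost nothing if the effect is confined to months 1–6 or 3–6. With a true effect of the planned size, the interaction is non-significant in 2% to 48% of trials (11% to 28% in the linear courses).

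The percentages rest on the Cohen's f reading, equal correlation between visits, complete data, a three-contrast family and the assumed courses. The mismatch of 2 against 10 df, and of two against six visits, rests on none of these. The main harm is lost power and the missing primary comparison, with little inflation of false claims.

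**What to change.** Amend the SAP, Analysis methods, Primary outcome, before the analysis:

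1. Keep the six-visit mixed model. Make the 2-df joint contrast of treatment by (month 6 minus baseline) the single primary test, and state that its p<0.05 alone decides whether the primary hypothesis is met.
2. Name exactly three difference-in-change contrasts: LSE–RSE, HSE–RSE and LSE–HSE. Calculate and report them with confidence intervals, Bonferroni adjusted over three, whatever the 2-df test or the all-visit interaction shows. They describe which arms differ and do not by themselves declare success.
3. Make the 10-df interaction and the comparisons at months 1, 3, 7 and 10 secondary, where the Outcomes table already places them.

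**Cost.** Wording only: same model, same data, no extra participants. The all-visit interaction loses its gatekeeping role, and the family-wise error of the pairwise 0–6 claims rises from about 1% to about 4%, still below 5%.

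The alternative is to keep the condition and recompute the sample size for the six-visit rule with a stated time course and covariance. In the courses for which this was calculated, that needs about 162 to 246 completers instead of 147.
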